9.3.1. Definition of clinical outcome measures

Real-world progression-free survival (PFS)

Real-world PFS is defined as the time from the start of treatment with avelumab plus axitinib to the date of first disease progression (as clinically assessed by a local investigator based on a radiology assessment, laboratory evidence, pathological data, and/or other assessments) or death due to any cause, which ever came first. If there are no clinical records of death or disease progression, patients will be censored at the date of initiation of the next line of therapy for those undertaking 2 or more lines of therapy based on the details in their medical records or at their last visit date during the study period for those undergoing only first line of therapy. However, if the nephrectomy is performed earlier than the above date, the data is to be treated as censored at the date of nephrectomy.

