### **5.1 EFFICACY/EFFECTIVENESS ENDPOINT(S)**

<Derivation of time-to-event variables>

Item	Derivation method
Real-world progression-free survival (PFS)	Defined as the period from the start date of avelumab plus axitinib combination therapy to

PFIZER CONFIDENTIAL

	
the date of first disease progression (clinical evaluation based on radiographic, clinical, and pathological examinations, as well as other evaluations by the principal investigator or co-investigator) or death from any cause, whichever occurs earlier. If there is no clinical record of death or disease progression, the following dates will be used for censoring, based on medical records:
 
 
(1) If first-line therapy is ongoing, the final progression-free confirmation date or the date of the last hospital visit, whichever is earlier, will be used for censoring.
 
(2) If second-line therapy has not been initiated after the end of first-line therapy, the final progression-free confirmation date or the date of the last hospital visit, whichever is earlier, will be used for censoring.
 
(3) If second-line therapy has been initiated, the date of initiating the second-line therapy will be used for censoring.
 
(4) If nephrectomy has been performed, the date of nephrectomy will be used for censoring.
 

Reasons for real-world PFS events	
Reasons for real-world PFS events are defined as follows:
 
"Disease progression after the initiation of avelumab plus axitinib combination therapy" will be selected if there was disease progression after starting avelumab plus axitinib combination therapy.
 
"Death" will be selected if the patient has died.

Reasons for censoring real-world PFS	
Reasons for censoring real-world PFS are defined as follows:
 
"No disease progression during or after first-line therapy" will be selected if first-line therapy is ongoing or if second-line therapy has not been initiated after the end of first-line therapy.
 
"Second-line therapy started" will be selected if second-line therapy has been initiated.
 
"Nephrectomy performed" will be selected if nephrectomy has been performed.

Overall survival (OS)	
Defined as the period from the initiation of avelumab plus axitinib combination therapy to the date of death from any cause. If there is no

PFIZER CONFIDENTIAL

CT24-WI-GL03-RF03 2.0 *Non-Interventional Statistical Analysis Plan For Secondary Data Collection*  

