**7.2.2.10 Subsequent treatment of avelumab plus axitinib combination therapy**

Source : FAS, Efficacy analysis set

population

Endpoints : Continuous variables

Second-line therapy period (days)

The period from the end date of first-line therapy to the beginning of second-line therapy (days)

Categorical variables

Performance of nephrectomy after avelumab plus axitinib combination therapy

Presence or absence of second-line therapy

Drug category

Second-line therapy regimen by drug category

Analysis : The following aggregation will be performed for the endpoints:  
content Summary statistics will be calculated for continuous variables.  
The period from the end date of first-line therapy to the beginning of second-line therapy (days) will also be estimated, considering the reason for termination of administration.  
A frequency table (number of cases, percentage (%)) will be created for categorical variables.

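### Real-world PFS is capped at the last progression-free confirmation under SAP rules (1)/(2) but not under rules (3)/(4), which overstates PFS if assessment stops before the switch

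*SAP*

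**What the plan says.** SAP 5.1 opens its censoring rules with a condition: "If there is no clinical record of death or disease progression, the following dates will be used for censoring, based on medical records". Four rules follow.

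- Rules (1) and (2) cover patients still on first line, or off it with no second line: "the final progression-free confirmation date or the date of the last hospital visit, whichever is earlier, will be used for censoring".
- Rule (3): "If second-line therapy has been initiated, the date of initiating the second-line therapy will be used for censoring".
- Rule (4): "If nephrectomy has been performed, the date of nephrectomy will be used for censoring".

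Protocol 9.3.1 has the same next-line rule: "patients will be censored at the date of initiation of the next line of therapy for those undertaking 2 or more lines of therapy". For everyone else it uses the last visit: "or at their last visit date during the study period for those undergoing only first line of therapy". On nephrectomy it adds: "However, if the nephrectomy is performed earlier than the above date, the data is to be treated as censored at the date of nephrectomy".

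The limit at the last progression-free confirmation is therefore a SAP addition, made for two of the four cases. The SAP gives no reason for the difference. SAP 7.2.2.2 reports the PFS median, the rate every 12 months and a table of censoring reasons. SAP 7.2.2.10 summarises the number of days between the end of first line and the start of second line. Neither document sets a tumour assessment schedule. No sensitivity analysis of these rules is visible, though parts of the SAP are redacted.

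**The concern.** The issue is which date is used, not who is censored. Suppose first line stops for an adverse event at month 4 and progression-free status is last confirmed that month. If no further therapy follows, PFS is censored at month 4. If second line starts at month 8, with nothing recorded in between, the same patient contributes 8 progression-free months. The extra 4 months come from the delay before the next drug, not from any evidence about the tumour.

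Real-world PFS is the first treatment outcome listed under the secondary objectives. If such gaps are common, its median and 12-monthly rates partly reflect how long patients wait for second line.

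**Working it through.** The documents state no expected PFS, event count or power, so there is no planned figure to reproduce. The check covers the text, the direction and the size.

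**Text**

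| Case (no recorded progression or death) | Protocol 9.3.1 | SAP 5.1 |
|---|---|---|
| First line only | Last visit | Earlier of last confirmation and last visit |
| Second line started | Next-line start | Second-line start, no look-back |
| Nephrectomy | Its date, if earlier | Its date, no look-back |

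An evaluation after the last confirmation either shows progression, which is an event, or shows none, which moves the confirmation date. For a patient who reaches rule (3), the interval from last confirmation to switch therefore holds no conclusive tumour assessment.

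**Direction.** The estimate is S(t) = ∏(1 − d/n) over event times. Moving some censoring dates later leaves every d unchanged and can only raise n. S(t) is then equal or higher. In 1,000 simulated studies of 150 patients, the 12- and 24-month rates under rule (3) were never below those under look-back.

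**Size if assessment stops before the switch: hand calculation.** Inputs:
- Median PFS 13.8 months (Protocol section 7, used as an assumption), exponential: h = ln 2/13.8 = 0.0502 per month. True 12-month PFS = exp(−12 × 0.0502) = 0.547.
- First line stops, unrelated to progression, at s = ln 2/40 = 0.0173 or ln 2/20 = 0.0347 per month (assumed).
- Gap g of 2 or 4 months with nothing recorded (assumed).

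For each patient still assessed, the risk set holds k = s(exp((h+s)g) − 1)/(h+s) patients who are in a gap. The estimated hazard is then h/(1+k) after month g, with about k/2 in place of k before it.

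- s = 0.0173, g = 2: k = 0.037. Cumulative hazard at 12 months = 0.0502 × (2/1.0185 + 10/1.037) = 0.583, so PFS = 0.558 (+1.1 points). Median = 2 + (13.8 − 2/1.0185) × 1.037 = 14.3.
- s = 0.0347, g = 4: k = 0.165. Cumulative hazard = 0.0502 × (4/1.0825 + 8/1.165) = 0.530, so PFS = 0.588 (+4.1 points). Median = 4 + (13.8 − 4/1.0825) × 1.165 = 15.8.

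**Size with visit-based assessment: simulation.** 400,000 patients per scenario, follow-up uniform over 6-34.4 months (index dates 20 December 2019 to 30 April 2022, followed to 31 October 2022), assessments every 1.5 or 3 months that end with first line, and 16-32% censored at the switch. The benchmark is the same cohort with nobody switching. It lies above 0.547 because progression is recorded only at the next visit.

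| 12-month PFS | Every 1.5 months | Every 3 months |
|---|---|---|
| Benchmark | 0.563 | 0.579 |
| Rule (3), no gap | 0.562-0.563 | 0.578-0.580 |
| Rule (3), gap 2-4 months | 0.573-0.601 | 0.590-0.619 |

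The excess with a gap is 1.0-3.8 and 1.1-4.0 points, or about 1-4. The median is about 0.3-1.8 months too high, the low end arising when deaths in the gap are counted as events. Look-back gives a 12-month rate of 0.553-0.571, closer to the true 0.547 than rule (3) in every gap scenario, and a 24-month rate of 0.277-0.296 against 0.300, slightly low.

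**Size if assessment continues to the switch.** Rule (3) matches the benchmark (0.563 against 0.563; about 0.580 against 0.579). With 12-30% switching, look-back lowers the 12-month rate by 0.2-1.4 points and the 24-month rate by 0.3-1.6.

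**Switching prompted by unrecorded progression.** If 20% of patients switch just after an unrecorded progression, rule (3) gives about 0.619 against 0.563, or 0.637 against 0.579. Look-back removes only 0.4-1.6 of that 5.5-5.8 point excess.

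**The case against.** A reader might infer that PFS is biased upward whatever happens, because a patient in the gap cannot have an event. The documents do not support that. The four rules apply only when no progression or death is on record, so either one recorded in the interval is an event on its own date. Progression may rest on clinical or other evaluation as well as imaging. If every progression and death in the gap is recorded, rule (3) returns the true median of 13.8 months. Look-back with the confirmation date left frozen then gives 13.4, 13.1, 13.0 and 12.4 across the four combinations of s and g, which is too low.

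That downward result needs charts that record every progression in the gap while no clean evaluation moves the confirmation date. If evaluations are made, some should be clean, and look-back then loses little. A milder form stands: deaths in the gap are captured while confirmations are not, so look-back can run somewhat low.

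Other points also stand:
- Rule (3) is the protocol's own rule. It is a choice of convention, not a slip in the SAP.
- Nephrectomy may precede the last confirmation. Rule (4) then shortens the credited time.
- The larger threat is informative switching, which a change of date only partly addresses.
- The study is descriptive and PFS is secondary. With 150 patients and assessment continuing (3-month visits, switching at 0.02 per month), the rules differ by 0.9 points at 12 months, against a sampling SD of 4.9.
- Censoring reasons and the first-to-second-line interval are tabulated, so a reader can see part of the problem.

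Sampling error does not dispose of the point: the shift is systematic, and the confidence interval does not reflect it.

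**Conclusion.** The inconsistency is real. Rules (1)/(2) credit only confirmed progression-free time, while rules (3)/(4) can also credit unconfirmed time, so the reported curve is equal to or higher than under one rule for all.

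The bias is conditional. It is near nil if assessment continues to the switch, and about 1-4 points at 12 months and 0.3-1.8 months in the median if assessment stops 2-4 months before it. Those sizes rest on exponential PFS with a 13.8-month median, stopping unrelated to progression, and 16-32% of patients censored this way. The documents give neither the gap nor the share. The change is worth making because it is cheap and makes the endpoint mean the same for all censored patients, not because a bias of known size has been shown.

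**What to change.** Change rules (3) and (4) in SAP 5.1 to censor at the earlier of the final progression-free confirmation date and the second-line start (or nephrectomy) date. Report the protocol's switch-date version as a sensitivity analysis, so that the spread between the two shows how much the unconfirmed time matters.

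The confirmation date is already needed for rules (1) and (2). Protocol 9.7 lets the SAP modify the planned analyses and ties amendments to major changes in primary endpoint definitions or analyses. Real-world PFS is secondary, so SAP wording suffices.

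The cost is slightly less follow-up time and a slightly low late PFS rate where assessment did continue to the switch. Where nephrectomy precedes the last confirmation, nothing changes. Bias from switching after unrecorded progression is only partly removed, and the report should say so.

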9.9. Limitations of the research methods

- This study is retrospective in nature. Therefore, only existing data reported in patient records is available for the present research. Missing data may affect the estimation accuracy.
- High-volume centers were preferentially selected for this study, potentially leading to site selection and outcome reporting biases. Therefore, the study results may not accurately reflect clinical outcomes for all Japanese centers.
- The evaluation of disease response may differ at each site, and measurement errors may be included in the estimated values.

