### **Analysis of secondary objectives**

#### **7.2.2.2 Real-world progression-free survival**

Source : Efficacy analysis set  
 population  
 Endpoint : Real-world PFS  
 Analysis content : For the endpoint, the median and its 95% confidence interval will be calculated using the Kaplan–Meier method. In addition, the Kaplan–Meier curve will be plotted, and the PFS rate for every 12 months and its 95% confidence interval will be calculated. Greenwood’s formula will be used to calculate the confidence interval for the PFS rate. In addition, the number of event-onset cases and the number of censored cases will be presented. A frequency table (number of cases, percentage (%)) will be created, considering the reasons for the event and reasons for censoring. In order to evaluate the observation period, the median observation period and its 95% confidence interval will be calculated by estimating the reverse Kaplan-Meier curve in which censoring patients are regarded as patients with events and patients with events are regarded as censoring patients.

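### Real-world PFS censors a switch to second-line therapy without recorded progression as if it were non-informative, and no readable sensitivity analysis shows how far this moves the estimate

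*SAP*

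**What the plan says.** SAP 5.1 opens its PFS censoring rules with a condition: "If there is no clinical record of death or disease progression, the following dates will be used for censoring, based on medical records". Rule (3) under it reads: "If second-line therapy has been initiated, the date of initiating the second-line therapy will be used for censoring". Protocol 9.3.1 agrees: "patients will be censored at the date of initiation of the next line of therapy".

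Progression is defined broadly in Protocol 9.3.1: "as clinically assessed by a local investigator based on a radiology assessment, laboratory evidence, pathological data, and/or other assessments".

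The estimator in SAP 7.2.2.2 is ordinary Kaplan–Meier: "the median and its 95% confidence interval will be calculated using the Kaplan–Meier method". The same section adds: "A frequency table (number of cases, percentage (%)) will be created, considering the reasons for the event and reasons for censoring". A switch to second-line therapy is one of the censoring reasons in that table. The readable text plans no sensitivity analysis for this rule; parts of the SAP are blacked out.

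Reasons for stopping first-line treatment are collected and used elsewhere, in TTD (SAP 5.1 and 7.2.2.6) and treatment patterns (SAP 7.2.2.7). Disease progression and adverse event are separate categories there. The PFS rule does not use them.

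**The concern.** Kaplan–Meier gives a censored patient the same later risk as those still under observation. A change of therapy is unlikely to be independent of prognosis: apart from efficacy, the reasons the SAP lists for ending first-line treatment are progression, adverse event and other. If a physician acted on a failing first-line regimen but the chart holds no progression entry, the failure enters the PFS analysis as a censoring.

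The plan can therefore classify one patient in two ways. Someone whose recorded stop reason is disease progression is a TTD event, yet without a charted progression or death the PFS rules censor that patient at the start of second-line therapy.

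PFS is the first outcome listed under the secondary objectives, and in a descriptive study the estimate is itself the product. The planned confidence interval reflects sampling variation only and would not show this effect. Protocol 9.9 acknowledges that "The evaluation of disease response may differ at each site, and measurement errors may be included in the estimated values", but does not mention informative censoring.

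**Working it through.** The plan states no PFS rate, event count or switch rate, so there is no figure to reproduce. What follows is an illustration.

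**Inputs from the documents.** Observation ends on 31 October 2022. The efficacy set needs an index date before 30 April 2022, so potential follow-up runs from about 6.0 to 34.4 months. About 150 patients are expected in total (Protocol 9.5). The median of 13.8 months is the phase 3 figure in Protocol section 7, used here for scale only.

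**Assumptions.** Exponential PFS, uniform entry, the share f of first-line failures that are switched but uncharted, the delay to any later recorded event, and the rate of switches unrelated to failure. The documents give none of these.

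**Truth under the assumptions.** λ = ln 2 / 13.8 = 0.0502 per month. 12-month PFS = exp(−12 × ln 2 / 13.8) = 54.7%.

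**A. Uncharted failures, no later event recorded (worst case).** The Kaplan–Meier hazard becomes λ(1 − f), so the median is 13.8/(1 − f) and 12-month PFS is 0.547^(1 − f).
- f = 10%: 13.8/0.9 = 15.3 months; 58.1%.
- f = 20%: 13.8/0.8 = 17.25 months; 61.7%.

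**B. Uncharted failures, later events counted.** Read literally, SAP 5.1 keeps a progression or death recorded after the switch as an event on its own date. Simulation with 400,000 patients, the later event arriving at a median of 6 or 12 months after the switch:

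| f | Share of all patients | 12-month PFS | Median, months |
|---|---|---|---|
| 10% | about 6% | 56.8–57.4% | 14.6–14.9 |
| 20% | about 12% | 58.9–60.1% | 15.4–16.0 |

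The upward bias shrinks but remains. Over A and B together, it is 2.1 to 3.4 points at f = 10% (56.8 − 54.7 and 58.1 − 54.7) and 4.2 to 7.0 points at f = 20% (58.9 − 54.7 and 61.7 − 54.7).

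**C. Switches unrelated to failure.** With a switch hazard of 0.008 per month, about 9% of patients switch before progression. The SAP rule then gives about 53.9% and 13.4 months, slightly below the truth: switchers with a later event stay in as events, while event-free switchers are cut short at the switch. If every switcher were censored at the switch regardless of later events, the result would be 54.7% and 13.8 months, with no bias.

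**D. Counting the switch as an event.** If every such switch is a true failure, this restores 54.7% and 13.8 months. In scenario C the hazard becomes 0.0502 + 0.008 = 0.0582, which gives a median of ln 2 / 0.0582 = 11.9 months and a 12-month PFS of 49.7%.

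**Scale.** With index dates spread evenly, the efficacy set would be about 150 × 862/1,033 = 125 patients (862 and 1,033 are the eligible index days for the efficacy set and the FAS). The simulated standard error of 12-month PFS is then about 4.6 points.

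**The case against.** The strongest reply is that the documents do not show any overstatement. Progression rests on broad investigator judgement, so a progression that was acted on can be an event without radiology. The eCRFs are queried and remotely monitored (Protocol 9.6 and 9.8). Events recorded after the switch still count. Scenario C moves the estimate down. Switch-censored patients will be counted, stop reasons are tabulated, and TTD in the same efficacy set already treats stopping for progression or adverse event as an event. PFS is secondary and descriptive, no hypothesis is tested, and further analyses may lie in the blacked-out text.

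Much of this stands. It rules out a claim about direction and limits how much is at stake. It does not remove the point. A count of censorings does not show how far the median or the 12-month rate moves. TTD is a different endpoint: it counts stops for intolerance whether or not second-line therapy follows, and it does not show what PFS would be under another status for the switch.

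A reader might also infer that the SAP curve and a switch-as-event curve bracket the true PFS, or that the gap between them measures the bias. Neither holds. In scenario C both curves (53.9% and 49.7%) lie below 54.7%. Of the 4.2-point gap, the SAP rule is only 0.8 points from the truth; the switch-as-event curve is 5.0 points from it.

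**Conclusion.** The point holds as a conditional risk. The plan treats a switch without recorded progression as non-informative, has the stop reason available but does not use it for PFS, and offers no readable analysis of the consequence. Under the illustrative model, 12-month PFS is too high by about 2 to 3 points if 10% of failures are uncharted, and by about 4 to 7 points if 20% are. It is too low by about 1 point if 9% of patients switch for unrelated reasons. Against a standard error of about 4.6 points, these range from negligible to larger than sampling error.

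It is tempting to conclude that the planned PFS is overstated. The documents do not support that: they give neither a switch rate nor an under-charting rate, and the net direction depends on the mix. The figures rest on exponential PFS with the phase 3 median, uniform entry, and failures that go uncharted at random. No decision rule or sample size is affected. Because the direction is unknown, the case is for a sensitivity analysis rather than a change to the main definition.

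**What to change.** Keep the SAP 5.1 definition as the main analysis. Add to SAP 7.2.2.2 a sensitivity Kaplan–Meier analysis in which the start of second-line therapy without a prior recorded progression is a PFS event on its start date, with the other rules unchanged:

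- (a) for all such switches, labelled as a conservative lower-bound analysis;
- (b) only for those whose recorded first-line stop reason is disease progression, stating which reason applies if avelumab and axitinib were stopped for different ones.

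Report medians and 12-monthly rates from (a) and (b) beside the main result. Cross-tabulate switch-censored patients by first-line stop reason. Name informative censoring as a limitation in the report. Do not describe the curves as bracketing the true PFS.

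The cost is a few sentences in the SAP, two extra curves and one table, all from data already collected. Protocol 9.7 requires the SAP to be fixed before data lock, so an analysis added later should be labelled post hoc. The downside is a less favourable companion figure, and version (a) will count some tolerability switches as failures.

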9.3.1.1. Overall Survival (OS)

OS is defined as the time from the start of treatment with avelumab plus axitinib to the date of death due to any cause. If there are no clinical records of death, the date when the patient was last documented to be alive will be confirmed based on medical records. The data will be censored at the date of last contact.

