9.4. Data sources

As this is a retrospective study, all data are to be collected from the patient medical records at the participating study sites.

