10.2.2. Patients who are alive and were transferred to another medical facility

Investigators must obtain oral informed consent for data collection from each patient who was transferred to another hospital before data collection. When obtaining oral informed consent, the investigator will document the method and content of the explanation as well as the details of the obtained consent.

When it is difficult to obtain oral informed consent for the following reasons, consent will not be required based on the Act on the Protection of Personal Information Article 27 (1) - (iii) and the Frequently Asked Questions related to the article:

- The study site does not obtain valid patient contact information.
- When considering the time available and research costs incurred in obtaining oral informed consent at the study site, it is concluded that obtaining oral informed consent at the study site could significantly impact the conduct of the study.

Even in these cases, the study information must be disclosed, and the patients' legally acceptable representatives will be guaranteed an opportunity to refuse to provide patient data to the sponsor.

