*Study 01-Jun-2020*  
 Page 8 of 30

	record of death, the date when the survival of the patient was last confirmed on record (date of last hospital visit) will be used for censoring.
Time to treatment discontinuation (TTD) of avelumab plus axitinib combination therapy as first-line therapy	Defined as the period from the date of initiation of avelumab plus axitinib combination therapy to the date of ending treatment* for any reason (excluding discontinuation due to efficacy). In the case of discontinuation due to efficacy, the date of last administration will be used for censoring. If treatment has not ended, the date of the last hospital visit will be used for censoring. * The end date of treatment is the date of last avelumab administration + 13 days or the date of last axitinib administration, whichever occurs later, or the data-cut date, if performed earlier.
TTD of avelumab as first-line therapy	Defined as the period from the date of initiation of avelumab to the date of ending administration* for any reason (excluding discontinuation due to efficacy). In the case of discontinuation due to efficacy, the date of the last avelumab administration will be used for censoring. If treatment has not ended, the date of the last hospital visit will be used for censoring. * The end date of avelumab therapy is the date of the last avelumab administration + 13 days or the data-cut date, whichever occurs earlier.
TTD of axitinib as first-line therapy	Defined as the period from the date of initiation of axitinib to the date of ending administration* for any reason (excluding discontinuation due to efficacy). In the case of discontinuation due to efficacy, the date of the last axitinib administration will be used for censoring. If treatment has not ended, the date of the last hospital visit will be used for censoring. * The end date of axitinib is the date of the last axitinib administration.
Reasons for the TTD event	Reasons for TTD event are defined as follows: Disease progression/adverse event/other (death)/other (excluding death)
Reasons for censoring TTD	Reasons for censoring TTD are defined as follows: "Treatment ongoing" will be selected if the treatment is ongoing.

PFIZER CONFIDENTIAL

CT24-WI-GL03-RF03 2.0 *Non-Interventional Statistical Analysis Plan For Secondary Data Collection*  
 Study 01-Jun-2020  
 Page 9 of 30

	" discontinuation due to efficacy " will be selected in case of discontinuation due to efficacy.
--	--

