#### 【Division of categorical variables】

Factor	Category
Reasons for the event (cause of death)	Death from primary disease; Death related to avelumab plus axitinib combination therapy; Death not related to avelumab plus axitinib combination therapy
Reasons for censoring	Survival; Untraceable

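### The SAP narrows the protocol's OS censoring date from last contact to last hospital visit but still counts later deaths, so OS may be biased, in a direction the documents do not settle

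*SAP*

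**What the plan says.** Protocol 9.3.1.1 handles a patient with no recorded death in two steps. First, "the date when the patient was last documented to be alive will be confirmed based on medical records". Then, "The data will be censored at the date of last contact".

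The OS row of SAP 5.1 opens with the same idea but ends differently: the date on which survival was "last confirmed on record (date of last hospital visit) will be used for censoring". The parenthesis turns a last-known-alive date into a visit date.

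The event side has no matching limit. OS is "Defined as the period from the initiation of avelumab plus axitinib combination therapy to the date of death from any cause", and nothing requires the death to fall on or before the last visit. The observation period ends on 31 October 2022 in both documents. The OS row does not apply that date, although the SAP's TTD rows for the combination and for avelumab do carry a data-cut limit.

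Patients who left the site are expected. Protocol 10.2.2 is headed "Patients who are alive and were transferred to another medical facility", and SAP 7.2.2.3 lists the OS censoring reasons as "Survival; Untraceable". On sources, Protocol 9.4 states that "all data are to be collected from the patient medical records at the participating study sites".

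**The concern.** The last visit and the last date known alive differ for patients who moved to another facility. They also differ slightly for those still attending, because the last visit usually precedes the cut-off. Suppose the chart shows what happened after the last visit. If it shows a death, that time and that event enter the analysis. If it shows the patient alive, the time is dropped. Whether follow-up counts would then depend on the outcome, and a Kaplan-Meier estimate assumes that it does not.

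The OS median and the 12-monthly survival rates are at stake, and so is the reverse Kaplan-Meier follow-up, which becomes shorter. OS is a named secondary outcome. The study is descriptive, so no test or power is affected.

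**Working it through.** The documents contain no OS, event or sample-size calculation to reproduce. The check is a short argument for the direction, followed by a simulation for the scale.

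**Direction.** Consider only the time after each patient's last visit. Let D be the recorded deaths in that time, Y_D the person-time of those who died, and Y_S the person-time of those later documented alive.

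- Last-contact rule: hazard = D / (Y_D + Y_S).
- SAP rule: hazard = D / Y_D.
- Ratio of SAP to last contact = (Y_D + Y_S) / Y_D, which exceeds 1 whenever D > 0 and Y_S > 0. The SAP rule then gives the lower OS.
- If no later deaths are recorded (D = 0), the SAP rule drops this time altogether. That is harmless if leaving is unrelated to prognosis, and too favourable if leavers die sooner. The last-contact rule then credits Y_S with no deaths, which is also too favourable.

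The direction therefore turns on how completely later deaths are captured.

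**Inputs from the documents.** The OS population has index dates from 20 December 2019 to 29 April 2022, with cut-off at 31 October 2022. Using the SAP's day count and its month of 30.4375 days, the longest follow-up is 1,047 / 30.4375 = 34.4 months and the shortest is 186 / 30.4375 = 6.1 months. About 150 patients are expected in total.

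**Assumptions, not in the documents.**

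- Follow-up is uniform over 6.1 to 34.4 months, and OS is exponential with 24-month survival of 60%, 70% or 80%.
- Between 0% and 30% of patients leave the site, at a uniform time.
- A leaver's later death is known with probability q, and a surviving leaver has a later contact with probability c.
- Those who stay have their last visit 0 to 1 month before cut-off.
- There are 400,000 simulated patients per scenario.

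**Bias in 24-month OS, percentage points (70% baseline, 20% leaving).**

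| Leavers | q | c | SAP rule | Last contact |
|---|---|---|---|---|
| Same hazard | 1 | 1 | -3.0 | +0.1 |
| Same hazard | 0.5 | 0.5 | -1.8 | +0.2 |
| Same hazard | 0 | 0 | -0.5 | 0.0 |
| Same hazard | 0 | 1 | -0.6 | +2.8 |
| Twice the hazard | 1 | 1 | -2.6 | +0.2 |
| Twice the hazard | 0.5 | 0.5 | -0.4 | +1.5 |
| Twice the hazard | 0 | 0 | +2.0 | +2.5 |
| Twice the hazard | 0 | 1 | +2.1 | +5.5 |

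**Range for the SAP rule.**

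- q = c = 1, same hazard, 24-month OS of 60% to 80%: -1.3 to -2.1 with 10% leaving, -2.4 to -3.6 with 20%, and -3.4 to -5.2 with 30%.
- q = 0, random leaving: -0.3 to -0.7.
- q = 0, leavers with twice the hazard (70% baseline), 10% to 30% leaving: +0.8 to +3.4.
- No one leaving (70% baseline), visit gap alone: -0.3, -0.5 and -1.7 for gaps of up to 0.5, 1 and 3 months.

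**Scale.** The simulated standard error of 24-month OS with 150 patients is about 4.6 points, so the 95% CI half-width is 1.96 × 4.6 = 9.0 points.

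**The case against.** A reader might infer that OS is biased downward as a matter of fact. The documents do not support that. It requires sites to learn of deaths after the last visit. The only source is the participating sites' own records, and no registry linkage or active tracing is described. The consent sections separate attending, transferred and deceased patients, so sites must form some view of vital status. That makes knowledge of some later deaths plausible, but it does not show how complete the knowledge is.

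A second tempting inference concerns the consent procedure: "Investigators must obtain oral informed consent for data collection from each patient who was transferred to another hospital before data collection". Collection was planned from 15 December 2022, so a patient reached then was alive at the cut-off, and crediting that follow-up may seem the obvious repair. It is unsafe alone. Such contacts select survivors, and Protocol 10.2.2 waives consent where contact details are missing or the burden is too great. If leavers' deaths go unseen, the table shows +2.8 points, or +5.5 with doubled hazard, which is worse than the SAP rule.

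Three further points can be made for the plan. The SAP's leading words agree with the protocol, and only the parenthesis narrows them. With charts as the sole source, last visit may equal last contact for most patients. Protocol 9.7 lets the SAP modify the protocol. These lower the likely size, but they do not explain the narrowing or the absence of a matching limit on deaths. A programmer would implement the parenthesis.

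**Conclusion.** The two documents give different OS censoring dates, and the SAP version can make censoring depend on outcome. OS may be underestimated if records capture deaths after the last visit while later evidence of survival is set aside. In the random-leaving scenarios with both fully known, the shortfall at 24 months is 1.3 to 5.2 points for 10% to 30% leaving. If leavers' deaths are not captured, the effect is negligible under random leaving, or upward by 0.8 to 3.4 points when leavers have twice the hazard.

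The proportion leaving, the OS level and the completeness of death capture are all assumptions, so none of these figures predicts the bias in this study. Every SAP-rule shift lies inside the roughly 9-point half-width of the interval, but a systematic shift is not reflected in that interval. The last-contact rule is the better default because it is the protocol's own and is close to unbiased when deaths and survival are equally well known. It is not a safeguard when they are not.

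**What to change.** In the OS row of SAP 5.1:

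1. Delete the parenthesis naming the hospital visit, and censor at the last date the patient is documented alive in the site's medical records, as in Protocol 9.3.1.1.
2. Apply the 31 October 2022 cut-off to deaths and last-alive dates alike. A patient who dies later is censored at the cut-off.
3. Do not extend follow-up through contacts made only for consent unless deaths among patients who left are ascertained equally.
4. Report OS under last-visit censoring as a sensitivity analysis.

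A sentence on how sites learn of death or survival after the last visit would let readers judge the likely direction of any bias.

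The cost is SAP wording and one extra run, with no added patients. One constraint remains: the SAP took effect on 22 May 2023, after the planned end of data collection on 30 April 2023. If last-alive dates other than visits were not collected, state that as a limitation of the OS estimate.
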